### **1.1.1 Non-clinical Pharmacology**

Non-clinical pharmacology studies have demonstrated that PB2452 binds with high affinity and selectivity to the P2Y12 receptor antagonist ticagrelor and its active metabolite, TAM, (equilibrium dissociation constant  $K_D$  20 pmol/L). PB2452 rapidly neutralizes the unbound plasma fraction of ticagrelor and TAM, thereby reversing ticagrelor- and TAM-mediated inhibition of adenosine diphosphate (ADP)-induced platelet aggregation in a concentration- and dose-dependent manner in vitro (in human platelet-rich plasma) and in vivo (mouse and pig, dose-dependency data in mouse only). In mice dosed with ticagrelor to a supratherapeutic plasma exposure, those dosed with PB2452 before a tail cut had reduced bleeding to a degree not statistically different from the observation in mice not treated with ticagrelor. The activity in vitro and the rapid onset of effect observed in vivo translated to a reduction of bleeding in ticagrelor-treated mice to a degree that was not statistically significantly different from mice not treated with ticagrelor. Detailed descriptions of the non-clinical pharmacology of PB2452 may be found in the Investigators' Brochure (IB) for PB2452.

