### **1.1.3 Benefit/Risk Assessment**

The first in human study of PB2452 in healthy volunteers (PB2452-PT-CL-0001) demonstrated that PB2452 appears to be generally safe and well tolerated when administered intravenously across a dose range of 0.1-18 g. The healthy volunteers who were 18-50 years in age were not expected to nor received any benefit from administration of PB2452. Platelet function analyses showed that PB2452 delivered immediate and sustained reversal of ticagrelor, occurring as early as 5 minutes after initiation of PB2452 infusions and lasting for 20-24 hours. Rapid and sustained ticagrelor reversal by PB2452 may provide clinically significant benefit in patients taking ticagrelor who experience serious bleeding or require urgent surgical procedures by supporting rapid hemostasis or prevention of procedure-related bleeding.

Although treatment emergent adverse events associated with PB2452 in the Phase 1 study were mostly mild and infrequent with no infusion-related or hypersensitivity reactions observed, in the older and elderly subjects in this Phase 2A study, there remain potential risks of infusion-related reactions (IRRs), infusion site reactions, and hypersensitivity-type reactions which can result from exposure to recombinant protein drugs administered intravenously (IV). These risks may be mitigated by predefined exclusion criteria and by close monitoring during and after administration. Risks may also be mitigated by premedication prior to receiving PB2452 which will be implemented if a study subject develops a Grade  $\geq 2$  IRR.

The older and elderly subjects in this study will be administered dual anti-platelet therapy with ASA and ticagrelor which carries a risk of bleeding. The bleeding risk in study subjects is considered very low because the duration of dual antiplatelet therapy is only 48 hours. Among those patients taking ticagrelor for therapeutic benefit, the potential risk of disease-related thrombosis upon reversal of the antiplatelet effect of ticagrelor will be evaluated in future clinical studies and by thorough monitoring of hemostasis parameters. In the current study, three platelet function assays and multiple platelet agonists will be used to monitor platelet function which will demonstrate both the reversal profile of PB2452 and also a potential prothrombotic rebound increase in platelet function. The risk of a platelet rebound effect is considered low and was not observed in the Phase 1 study.

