10.1.1. Plasma Pharmacokinetics Concentration

Throughout this document, the total MEDI2452 (PB2452) includes free MEDI2452 (PB2452), protein-bound MEDI2452 (PB2452), ticagrelor-complexed MEDI2452 (PB2452), and TAM-complexed MEDI2452 (PB2452). The unbound MEDI2452 (PB2452) includes free MEDI2452 (PB2452) and protein-bound MEDI2452 (PB2452). Similarly, total ticagrelor (or TAM) includes free ticagrelor (or TAM), protein bound ticagrelor (or TAM), and MEDI2452 (PB2452)-complexed ticagrelor (or TAM). The unbound ticagrelor (or TAM) includes free ticagrelor (or TAM).

Blood samples for PK analysis of total and unbound PB2452 concentration in plasma will be collected from all subjects at the following time points: before dosing (0 hour) and up to 28 days after initiation of the study drug (PB2452 or placebo) infusion. Collection time points for cohorts were be specified in a Dosing Memo from Sponsor prior to initiation of each cohort, and are provided below.

Collection times relative to the initiation of the study drug (PB2452 or placebo) infusion on Day 1 were: Hour 0 (up to 10 minutes prior to PB2452 infusion), 5 minutes, 0.25, 0.5, 1, 2, 4, 8, 12, 20, 24, 36, 48 hours, and 7 and 28 days post-dose.

Plasma samples for determining total and unbound concentrations of ticagrelor and its active metabolite TAM, will be collected at the following timepoints: before dosing (within 10 minutes prior to the initiation of the study drug infusion [Hour 0]), and up to 28 days following the initiation of PB2452 or placebo infusion on Day 1. Subjects will be administered the 5th ticagrelor dose two hours before the study drug infusion initiation on Day 1.

Specific collection times relative to the initiation of the study drug (PB2452 or placebo) infusion were: Hour 0 (up to 10 minutes prior to PB2452 infusion), 5 minutes, 0.25, 0.5, 1, 2, 4, 8, 12, 20, 24, 36, 48 hours, and 7 and 28 days post-dose.

Concentrations that are below the limit of quantification (BLQ) will be treated as zero for descriptive statistics. Mean BLQ concentrations will be presented as BLQ, and the SD and

coefficient of variation (CV) will be reported as not applicable. Missing concentrations will be excluded from the calculations.

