10.1.2. Plasma Pharmacokinetic Parameters

The PK parameters of PB2452, ticagrelor, and TAM will be determined using noncompartmental methods using Phoenix WinNonlin Version 8.0 or higher or SAS® Version 9.4 or higher. For PK analysis, BLQ values will be treated as zero with the exception that a BLQ value between 2 quantifiable concentrations will be set as missing. If consecutive BLQ concentrations are followed by quantifiable concentrations in the terminal phase, those concentrations after BLQ concentrations will be treated as missing. Missing concentrations will be treated as missing from the PK parameter calculation

The following PK parameters, if data permit, will be calculated for total and unbound plasma PB2452 using actual sampling times.

PB2452 PK parameters:

Parameter	Description
C_{\max}	Observed maximum plasma concentration
T_{\max}	Time to reach the observed maximum plasma concentration
AUC_{0-t}	Area under the plasma concentration versus time curve (AUC) from time 0 to the time of last quantifiable concentration (C_{last}); calculated using the linear-up/ log-down trapezoidal rule
$AUC_{0-\infty}$	AUC from time 0 extrapolated to infinity, calculated as $AUC_{0-t} + C_{\text{last}}/\lambda_z$, where C_{last} is the last quantifiable plasma drug concentration and λ_z is the terminal phase rate constant.
AUC_{0-24}	AUC from time 0 to 24 hours post-dose; calculated using the linear-up/log-down trapezoidal rule
AUC_{0-48}	AUC from time 0 to 48 hours post-dose; calculated using the linear-up/ log-down trapezoidal rule
%AUC _{extrap}	Percentage of $AUC_{0-\infty}$ due to extrapolation from the time for the last quantifiable concentration to infinity, calculated as $(AUC_{0-\infty} - AUC_{0-t})/AUC_{0-\infty} * 100$

λz	Terminal phase rate constant, determined by linear regression of the terminal points of the log-linear plasma concentration-time curve. The λz will not be estimated if the terminal phase of the log-concentration-time profile does not exhibit a linear decline phase, or if the regression coefficient (Rsq) is less than 0.8.
Rsq	Regression coefficient for calculation of λz
$t_{1/2}$	Terminal elimination half-life, calculated as $t_{1/2} = \ln(2) / \lambda z$.
CL	Total body clearance, calculated as Dose/AUC _{0-inf}
Vd	Volume of distribution, calculated as CL/ λz .

The following PK parameters, as appropriate and when data permit, will be calculated for total and unbound ticagrelor and TAM using actual sampling times:

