Ticagrelor/ TAM PK parameters:

Parameter	Description
C _{max}	Observed maximum plasma concentration
T _{max}	Time to reach the observed maximum plasma concentration
AUC _{0-t}	AUC from time 0 to the time of last quantifiable concentration (C _{last}); calculated using the linear-up/log-down trapezoidal rule
AUC _{0-inf}	AUC from time 0 extrapolated to infinity, calculated as AUC _{0-t} + C _{last} / λz , where C _{last} is the last quantifiable plasma drug concentration and λz is the terminal phase rate constant.
AUC ₀₋₂₄	AUC from time 0 to 24 hours post-dose; calculated using the linear-up/log-down trapezoidal rule
AUC ₀₋₄₈	AUC from time 0 to 48 hours post-dose; calculated using the linear-up/log-down trapezoidal rule
%AUCextrap	Percentage of AUC _{0-inf} due to extrapolation from the time for the last quantifiable concentration to infinity, calculated as (AUC _{0-inf} - AUC _{0-t}) / AUC _{0-inf} * 100
λz	Terminal phase rate constant, determined by linear regression of the terminal points of the log-linear plasma concentration-time curve. The λz will not be estimated if the terminal phase of the log-concentration-time profile does not exhibit a linear decline phase, or if the regression coefficient (Rsq) is less than 0.8.
Rsq	Regression coefficient for calculation of λz
$t_{1/2}$	Terminal elimination half-life, calculated as $t_{1/2} = \ln(2) / \lambda z$.

Additional PK parameters may be calculated, as necessary. Pharmacokinetic parameters will be listed by subject and summarized for each dose level using descriptive statistics (number of subjects, mean, SD, CV, median, minimum, and maximum), with the exception of %AUCextrap, λz and Rsq, which will be listed only. Geometric means will be reported for AUCs and C_{max}.

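### Generic BLQ rules applied to unbound ticagrelor and TAM can distort the exploratory unbound AUCs in the PB2452 arm, in either direction, if levels fall below the LLOQ and later return

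*SAP*

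**What the plan says.** SAP 10.1.2 gives the BLQ handling for noncompartmental parameters: "BLQ values will be treated as zero with the exception that a BLQ value between 2 quantifiable concentrations will be set as missing". The sentence after it reads: "If consecutive BLQ concentrations are followed by quantifiable concentrations in the terminal phase, those concentrations after BLQ concentrations will be treated as missing". Protocol 3.6.4 carries the same two sentences in Part A and Part B.

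Neither sentence is limited by analyte. The same SAP section lists parameters that "will be calculated for total and unbound ticagrelor and TAM using actual sampling times", and it defines AUC0-24 as "AUC from time 0 to 24 hours post-dose; calculated using the linear-up/log-down trapezoidal rule". AUC0-t and AUC0-48 use the same trapezoid.

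Sampling in SAP 10.1.1 is at Hour 0, just before the infusion, and then at "5 minutes, 0.25, 0.5, 1, 2, 4, 8, 12, 20, 24, 36, 48 hours", with further samples on Days 7 and 28. On the pretreatment it says: "Subjects will be administered the 5th ticagrelor dose two hours before the study drug infusion initiation on Day 1".

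For concentration summaries by time point, SAP 10.1.1 takes BLQ as zero without exception. The effect of PB2452 on unbound ticagrelor and TAM is an exploratory objective in both Parts (SAP 2.3).

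**The concern.** Setting an embedded BLQ to missing makes sense when a single low reading in a smooth profile is probably an assay failure. Unbound ticagrelor and TAM under PB2452 may not be that situation. Protocol 1.1.1 says that "PB2452 rapidly neutralizes the unbound plasma fraction of ticagrelor and TAM", and Protocol 1.1.3 describes Phase 1 platelet reversal as "occurring as early as 5 minutes after initiation of PB2452 infusions and lasting for 20-24 hours". Protocol 1.1.2 adds that PB2452 concentrations fall rapidly once the infusion ends.

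A plausible unbound profile in the active arm is therefore quantifiable at Hour 0, BLQ for many hours, then quantifiable again. Every BLQ in that stretch lies between two quantifiable values. A placebo profile that declines steadily from Hour 0 has no such stretch, because any BLQ would come at its end. The rule would then act on one arm only, and on the values that carry the effect.

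The second sentence does not settle the matter. Where it is applied, it removes the returning values instead. The SAP does not say which sentence governs a run of BLQs caused by PB2452, or what the terminal phase is for a profile that is suppressed and then recovers. At stake is whether the unbound AUCs agree with the concentrations from which they are computed.

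**Working it through.** The documents state no AUC figure for this point, so there is nothing of the plan's own to reproduce. The check applies the SAP's trapezoid to illustrative profiles on the SAP sampling times.

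**Inputs from the documents:** the sampling times, the linear-up/log-down rule and the two BLQ sentences.

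**Assumptions, not in the documents:** Hour 0 = 100 units in both arms; placebo declines with a half-life of 6, 8 or 10 h; the PB2452 arm is BLQ from 5 minutes until a return at 20, 24 or 36 h; it returns at 10%, 25%, 50% or 100% of the placebo value at that time.

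**Formulas.** A falling segment between positive values contributes (C1 − C2)(t2 − t1)/ln(C1/C2). A rising segment, or one that touches zero, contributes (C1 + C2)(t2 − t1)/2.

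**Worked case: half-life 8 h, return at 24 h at 50% of placebo.**
- Placebo at 24 h is 100 × 2^(−24/8) = 12.5, so the PB2452 arm returns at 6.25.
- Placebo AUC0-24 = (100 − 12.5) × 24/ln 8 = 1009.9.
- BLQ = 0, return kept: 100 × (5/60)/2 + 6.25 × (24 − 20)/2 = 4.17 + 12.5 = 16.67, which is 1.7% of placebo.
- First sentence (run set to missing, Hour 0 joined to 24 h): (100 − 6.25) × 24/ln 16 = 811.5, which is 80.4% of placebo.
- Second sentence (return set to missing, BLQs now trailing zeros): 4.17, which is 0.4% of placebo.
- Both sentences: only Hour 0 remains, so no AUC can be calculated.

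A reduction of about 98% would thus be reported as about 20%, or as more than 99%, or not at all.

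**Whole grid, AUC0-24 as % of placebo:**

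| Return level | BLQ = 0, return kept | First sentence | Second sentence |
|---|---|---|---|
| 50-100% of placebo | 0.4-16 | 76-100 | 0.4-0.5 |
| 10-25% of placebo | 0.4-4.4 | 46-78 | 0.4-0.5 |

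With a 12 h half-life the second-sentence figure is 0.3%. For AUC0-48 with a return at 50-100% of placebo, 1.6-30% becomes 72-100% under the first sentence.

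**Where the rules do no harm (half-life 8 h).** If unbound drug never returns, the BLQs are trailing zeros and the ratio is 0.4%, as it should be. If levels stay low but quantifiable (2% of Hour 0 up to 20 h, then 50% of placebo), neither sentence is triggered and the ratio is 5.8%.

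**Sensitivity to the substituted value.** In the worked case with LLOQ = 1 unit, replacing BLQ by LLOQ/2 gives 2.5% and by LLOQ gives 3.6%, against 1.7% with zero. The choice among these matters far less than whether the values are deleted.

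**The case against.** The trigger is not documented. No LLOQ is given, and no passage reports human unbound concentrations. The neutralisation statement is non-clinical, and the 20-24 h refers to platelet function, not concentration. Harm needs both a fall below the LLOQ and a later quantifiable return. All of this stands, and it makes the point conditional.

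The first sentence can also be read as covering a single isolated BLQ, since it is worded in the singular and the next sentence deals with consecutive values. On that reading, a run outside the terminal phase stays at zero and nothing is masked. This reading is defensible, but the SAP does not choose it, and the alternatives give very different results from one profile.

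A reader might infer that the plan hides the drug effect, or always biases towards no effect. The documents do not support that. The AUC difference vanishes completely only if levels return exactly to placebo; otherwise it shrinks. The second sentence pushes the other way. The neutralised period also remains visible in the listings, the time-point summaries (BLQ = 0) and the individual and mean plots.

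Finally, the objective is exploratory, the parameters are summarised descriptively without a formal test, and the PD endpoints do not use these rules. That limits the importance of the point but does not remove it: a concentration table near zero could stand beside an AUC near placebo.

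**Conclusion.** The concern holds in a conditional form. If unbound ticagrelor or TAM falls below the LLOQ after Hour 0 and later becomes quantifiable, SAP 10.1.2 does not give a dependable AUC. Depending on which sentence is followed, a true AUC0-24 of about 0.4-16% of placebo becomes about 46-100%, or about 0.3-0.5%, or cannot be calculated. The direction of error is therefore uncertain. The sizes rest on an assumed half-life, time of return and level of return, and on an LLOQ above the neutralised concentration.

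The exposure is confined to AUC0-t, AUC0-24 and AUC0-48 of the two unbound analytes and any terminal-phase estimates drawn from the same profiles. Subjects who stay quantifiable, or who never return, are unaffected. The change should be made because it costs little, but no primary or secondary conclusion depends on it.

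**What to change.** In SAP 10.1.2 and in section 3.6.4 of both protocols, add a rule for unbound ticagrelor and unbound TAM only:

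- BLQ values after the start of study drug count as zero, including when they lie between quantifiable values.
- Quantifiable values that return after a run of BLQs are kept.
- Neither the embedded-BLQ exception nor the terminal-phase deletion applies to these two analytes.
- The AUCs are repeated with LLOQ/2 in place of zero as a sensitivity analysis.

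Both sentences must be switched off. Removing only the embedded-BLQ exception would leave the terminal-phase deletion free to erase the return.

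The cost is one or two sentences, one noncompartmental setting and one extra run. If no subject shows the pattern, the primary results do not change, because trailing BLQs are already zero. The small downside is that a true isolated assay drop-out would count as zero for these two analytes.

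### Does the SAP's deletion of quantifiable values after a BLQ run risk erasing a real return of unbound ticagrelor and TAM?

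*SAP*

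**What the plan says.** SAP 10.1.2 gives three handling rules for PK parameters.

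- Default and exception: "BLQ values will be treated as zero with the exception that a BLQ value between 2 quantifiable concentrations will be set as missing".
- Late values: "If consecutive BLQ concentrations are followed by quantifiable concentrations in the terminal phase, those concentrations after BLQ concentrations will be treated as missing".
- Missing values stay out of the parameter calculation.

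Protocol 3.6.4 has the same rules for Part A and Part B. They cover every plasma analyte, including the unbound ones; the ticagrelor and TAM parameters, "as appropriate and when data permit, will be calculated for total and unbound ticagrelor and TAM using actual sampling times".

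The terminal phase is given no start time. Its only other use in SAP 10.1.2 is in the lambda-z rows: "Terminal phase rate constant, determined by linear regression of the terminal points of the log-linear plasma concentration-time curve". Those rows add that lambda-z is not estimated when the terminal phase shows no linear decline on the log scale, or when the regression coefficient is below 0.8. AUC0-t is the "AUC from time 0 to the time of last quantifiable concentration", and "Geometric means will be reported for AUCs" and Cmax.

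SAP 10.1.1 schedules late samples at "24, 36, 48 hours, and 7 and 28 days post-dose", after earlier ones from Hour 0 to 20 h. In the concentration summaries, BLQ values "will be treated as zero for descriptive statistics", and nothing after a BLQ run is removed. Each subject's concentration profile is plotted.

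**The concern.** For most drugs a quantifiable value after a BLQ run is a stray late result, and dropping it is sensible. Unbound ticagrelor and TAM under a neutralizing antibody fragment may behave differently. Protocol 1.1.1 says PB2452 binds up the unbound fraction. Protocol 1.1.3 reports reversal in Phase 1 from as early as 5 minutes and for 20 to 24 hours. Cohort 1 is infused over 16 hours. A plausible active-arm profile is therefore quantifiable at Hour 0, then BLQ, then a return on the 20 to 48 h samples. Placebo subjects have no such gap.

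Those returning samples are the last points on the curve. If they are already falling, a programmer might call them the terminal phase and delete them. AUC would then be close to zero. If Hour 0 were the last quantifiable value left, AUC0-t would be exactly zero, its geometric mean could not be computed, and lambda-z would have no points. The by-dose AUC summary for the unbound analytes would depend on a coding choice.

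**Working it through.** The plan states no figure to reproduce here; SAP 4.1 says the sample size rests on practical grounds. The check is an illustration and a comparison of the texts.

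**Inputs from the documents.** Sampling times 0, 5 min, 0.25, 0.5, 1, 2, 4, 8, 12, 20, 24, 36 and 48 h (SAP 10.1.1). Linear-up/log-down trapezoids (SAP 10.1.2), taken as linear into and out of a zero.

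**Assumptions, not in the documents.** Placebo declines from Hour 0 with half-life 6, 8 or 12 h. The active arm equals placebo at Hour 0, is BLQ from 5 min through 12 or 20 h, then returns at 5, 10, 20, 30, 60 or 100% of the placebo level. The quantification limit is 1, 2 or 5% of Hour 0.

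**One case by hand** (half-life 12 h, Hour 0 = 100, BLQ through 20 h, return at 25% of placebo, no limit applied to the later values).

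Active values: 24 h, 0.25 × 100 × 2^(−24/12) = 6.25; 36 h, 3.125; 48 h, 1.5625.

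- 0 to 5 min: (5/60) × (100 + 0)/2 = 4.17
- 20 to 24 h: 4 × (0 + 6.25)/2 = 12.50
- 24 to 36 h: 12 × (6.25 − 3.125)/ln 2 = 54.10
- 36 to 48 h: 12 × (3.125 − 1.5625)/ln 2 = 27.05

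AUC0-48 with the return kept: 97.8. With it deleted, only the first triangle is left: 4.17. Placebo: 100 × (1 − 2^(−48/12)) × 12/ln 2 = 1623. The active/placebo ratio is 97.8/1623 = 0.060 kept and 4.17/1623 = 0.003 deleted.

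**Whole grid.** There are 3 × 2 × 6 = 36 profiles per limit. Values below the limit are set to zero in both arms, and profiles whose first returning value is itself BLQ are dropped.

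| Limit, % of Hour 0 | Profiles left | AUC0-24 ratio, kept | AUC0-24 ratio, deleted | AUC0-24 fold (median) | AUC0-48 fold |
|---|---|---|---|---|---|
| 1 | 30 | 0.005–0.19 | 0.003–0.005 | 1.6–58 (5.4) | 3.4–136 |
| 2 | 23 | 0.007–0.19 | 0.003–0.005 | 2.2–58 (7.3) | 5.3–136 |
| 5 | 16 | 0.011–0.19 | 0.003–0.005 | 3.4–58 (11.0) | 8.6–136 |

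The maxima need a return at the full placebo level. With a return of 30% or less they fall to about 18-fold (AUC0-24) and 42-fold (AUC0-48). Protocol 1.1.2 reports that PB2452 raises the renal clearance of ticagrelor and TAM, which argues against a full return. The folds are also large because the deleted area is only the triangle from Hour 0 to 5 minutes.

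**Which reading the text supports.**

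1. The default is zero. The exception is for one BLQ value between two quantifiable ones, so a long run stays at zero.
2. The deletion rule needs the terminal phase, which the lambda-z rows associate with a log-linear decline. In the scenario the BLQ run begins at 5 minutes, straight after Hour 0, with no decline before it.
3. Deletion undoes itself: it names the returning samples as the terminal phase and then removes the points that would define it.
4. Of the 30 + 23 + 16 = 69 retained profiles, 19 have one returning quantifiable value and so no slope. Another 25 have two, through which any line fits exactly. Only 25 have three or more.

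The plain result is that the run counts as zero and the return is kept.

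**The case for a change.** The strongest case for a change is that the sound reading is not secured. A return that is already falling from 24 to 48 h does look like a linear decline, and it is the end of the curve. Two competent programmers could differ, and the clause about data permitting lets a parameter be withheld without saying which rule to code. SAP 4.2 also lets named sponsor staff see unblinded data after each cohort's Day 3, so an open rule could be settled with results known.

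Part of this stands. The term is undefined, and under the assumed profiles the two codings give very different AUCs. What does not follow is an amendment. The trigger is an inference: the mechanism statement is nonclinical, and the 20 to 24 hours is platelet-function reversal, not unbound concentration. If unbound drug stays quantifiable, or does not come back by 48 h, nothing happens. If it does come back, the subject profiles, time-point summaries and scatter plots against PB2452 in SAP 10.1.1 all show it, so an AUC near zero beside a visible return would be noticed. No test uses these parameters.

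A full set of special rules for the unbound analytes would have costs of its own. Setting every BLQ value through 48 h to zero would remove the single-value exception; one isolated BLQ in a placebo profile would then lower AUC0-24 by up to about 23% on the same half-lives (lowest ratio 0.772, at 4 h with half-life 6 h). Reporting AUC0-t as not estimable when only Hour 0 is quantifiable would drop the most suppressed active subjects from the geometric mean and bias it upward. It would also put the SAP at odds with Protocol 3.6.4.

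**Conclusion.** This is missing detail that a PK analyst would be expected to fill correctly. The rule targets stray late values, the text read plainly keeps a genuine return, and the required plots would expose any other coding. The possible effect is large in relative terms (1.6- to 58-fold on AUC0-24, 3.4- to 136-fold on AUC0-48), but every input behind those figures except the sampling times and the trapezoid rule is assumed, and it arises only on a reading the text does not favour. It reaches only the derived parameters of unbound ticagrelor and TAM, which serve an exploratory objective (SAP 2.3) and are summarized descriptively. The plan can stand as written. The conclusion would weaken if assay data showed long BLQ runs with a return in many active subjects and the unbound AUCs were to carry a formal comparison; the documents indicate neither.
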